2.7. Section 5.0. Study Population

Prospective approval of protocol deviations to recruitment and enrollment criteria, also known as protocol waivers or exemptions, is not permitted.

Due to the criticality of participant health, verbal interview of the potential participant or their legal representative or family member, may be the source for disease characteristics and medical history, unless otherwise specified within the eligibility criteria.

2.7.1. Section 5.1. Inclusion Criteria

Participants are eligible to be included in this addendum only if all of the following criteria apply:

1. This criterion is not applicable to participants in this addendum
2. This criterion is not applicable to participants in this addendum
3. This criterion is not applicable to participants in this addendum
4. Must have first positive result sample of current SARS-CoV-2 viral infection ≤ 3 days prior to start of the administration
5. Are males or females
Reproductive and Contraceptive requirements are provided in the main PYAB protocol, Section 10.4, Appendix 4. Contraceptive use by males or females should be consistent with local regulations for those participating in clinical studies.
6. The participant and/or legally authorized representative understand and agree to comply with planned study procedures
7. The participant and/or legally authorized representative agree to the collection of nasopharyngeal swabs and venous blood
8. The participant or legally authorized representative give signed informed consent and/or assent as described in the main PYAB protocol, Section 10.1.3 which includes compliance with the requirements and restrictions listed in the informed consent form (ICF) and in this protocol.
27. This criterion is not applicable for participants in this addendum
28. This criterion is not applicable for participants in this addendum
36. Are 0 (≥ 38 weeks gestational age and ≥ 3.3 kg) to <12 years of age at the time of screening, or are 12 to 17 and weighing <40 kg.
37. Have mild to moderate COVID-19 disease, including one or more of the following symptoms, within the last 7 days (FDA February 2021; CDC January 2022; CDC March 2022.)
 - shortness of breath or difficulty breathing
 - fever
 - sore throat
 - nausea
 - diarrhea
 - nasal congestion or runny nose
 - chills
 - malaise
 - vomiting
 - cough

- tiredness
- headache
- new loss of taste
- muscle or body aches and pain
- new loss of smell, or
- poor appetite or poor feeding (especially in babies under 1 year old).

2.7.2. Section 5.2. Exclusion Criteria

Participants are excluded from this addendum if any of the following criteria apply:

9. SpO₂ ≤ 93% on room air at sea level, or while on chronic oxygen therapy and/or respiratory support due to underlying non-COVID-19 related comorbidity, respiratory rate ≥30 per minute, and heart rate ≥125 per minute due to COVID-19 (FDA February 2021)
10. Require mechanical ventilation or anticipated impending need for mechanical ventilation due to COVID-19
11. Have known allergies to any of the components used in the formulation of the interventions
12. Have hemodynamic instability requiring use of pressors within 24 hours of randomization
13. Suspected or proven serious, active bacterial, fungal, viral, or other infection (besides COVID-19) that in the opinion of the investigator could constitute a risk when taking intervention
14. Have any co-morbidity requiring surgery within 7 days, or that is considered life-threatening within 29 days
15. Have any serious concomitant systemic disease, condition or disorder that, in the opinion of the investigator, should preclude participation in this study.
16. This criterion is not applicable for participants in this addendum
17. This criterion is not applicable for participants in this addendum
18. This criterion is not applicable for participants in this addendum
19. Have received treatment with a SARS-CoV-2 specific monoclonal antibody or remdesivir within 90 days before dosing
20. Have received convalescent COVID-19 plasma treatment within 90 days before dosing
21. This criterion is not applicable for participants in this addendum
22. Have participated, within the last 30 days, in a clinical study involving an investigational intervention. If the previous investigational intervention has a long half-life, 5 half-lives or 30 days, whichever is longer, should have passed.
23. Are concurrently enrolled in any other type of medical research judged not to be scientifically or medically compatible with this study
24. Are currently pregnant or breast feeding
25. Are investigator site personnel directly affiliated with this study
29. This criterion is not applicable for participants in this addendum

31. Have a diagnosis of MIS-C in the opinion of the investigator
32. Are currently hospitalized for treatment of COVID-19. Other reasons for hospitalization are acceptable.

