available in vitro neutralization assays and pharmacokinetic (PK) data, this proposed study addendum intends to investigate the PK and safety of bebtelovimab in pediatric patients with COVID-19 <12 years of age or 12 to 17 years of age and weighing <40 kg.

[figure not shown]
2. Protocol Additions

Participants enrolled in this addendum will follow the specified sections in this addendum in place of the corresponding sections in the main PYAB protocol.

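### Exclusion 9 links its three signs with 'and', so it can be read as excluding SpO2 ≤93% only when both rate limits are also met; the SpO2 limit should be stated to exclude on its own

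*Protocol*

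**What the plan says.** The exclusion list in Protocol Section 2.7.2 (Section 5.2) opens with "Participants are excluded from this addendum if any of the following criteria apply". Criterion 9 is one numbered item. It gives SpO2 ≤93%, qualified as "on room air at sea level, or while on chronic oxygen therapy and/or respiratory support due to underlying non-COVID-19 related comorbidity", and then continues "respiratory rate ≥30 per minute, and heart rate ≥125 per minute due to COVID-19". It cites the FDA guidance of February 2021.

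Other criteria that bear on severity at entry are:

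- Inclusion 37 (Section 2.7.1) requires mild to moderate disease with at least one listed symptom. It cites the same guidance and prints no vital-sign limit.
- Exclusion 10: "Require mechanical ventilation or anticipated impending need for mechanical ventilation due to COVID-19".
- Exclusion 15: "Have any serious concomitant systemic disease, condition or disorder that, in the opinion of the investigator, should preclude participation in this study".
- Exclusion 32: "Are currently hospitalized for treatment of COVID-19".

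On which text governs, Protocol Section 2 states: "Participants enrolled in this addendum will follow the specified sections in this addendum in place of the corresponding sections in the main PYAB protocol". Section 2.7 rules out eligibility waivers, and the Schedule of Activities has sites confirm eligibility before treatment assignment and dosing.

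**The concern.** The population is meant to have mild to moderate disease, and criterion 9 is the only place where the addendum sets an oxygen-saturation limit. If that limit takes effect only together with two other signs, a hypoxic child whose breathing and heart rates are below the limits is not stopped by it. Entry would then depend on criteria that rest on clinical judgement.

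The entry check matters because follow-up just after dosing is light. Monitoring lasts at least 1 hour, Days 2 to 4 are telephone or virtual contacts, and the next scheduled vital signs are on Day 5. Two sites could also decide differently about the same child, each with a defensible reading.

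**Working it through.** No trial figure is at issue, so this is a check of wording and logic.

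**1. What each connective links.** The 'any' in the lead-in works across numbered criteria; it does not reach inside one. The 'or' in the SpO2 clause separates two conditions of measurement. The vital-signs row of the Schedule of Activities uses the same pair to say how screening SpO2 is taken. The only word left to join the three signs is 'and'.

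**2. Outcomes of the two readings.** Let S = SpO2 ≤93%, R = respiratory rate ≥30 and H = heart rate ≥125, each yes or no. That gives 2 × 2 × 2 = 8 combinations, 4 of them with S = yes:

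| R | H | S and R and H | S alone |
|---|---|---|---|
| yes | yes | excluded | excluded |
| yes | no | not excluded | excluded |
| no | yes | not excluded | excluded |
| no | no | not excluded | excluded |

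- All three required: 1 of 4 excluded, 3 of 4 left to other criteria (1 of 8 overall).
- SpO2 alone: 4 of 4 excluded (4 of 8 overall). The added 4 − 1 = 3 combinations all have SpO2 ≤93%.

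As an illustration, a child with SpO2 90%, respiratory rate 28 and heart rate 120 is not excluded under the first reading and is excluded under the second.

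**3. Why not simply change 'and' to 'or' throughout.** With S or R or H, 7 of 8 combinations are excluded. The added 7 − 4 = 3 all have SpO2 above 93%, so this step does nothing for hypoxia. It would make a heart rate of 125 an exclusion at every age. SAP Table PYAB.6.10 sets its high-pulse limits as follows:

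| Age band | SAP high pulse | 125 relative to it |
|---|---|---|
| <2 years | >190 | 65 below |
| 2–4 | >160 | 35 below |
| 5–9 | >150 | 25 below |
| 10–12 | >140 | 15 below |
| Adolescent | >120 | 5 above |

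The SAP limits also require a rise from baseline and serve a different purpose, so they are a guide to scale, not proposed entry limits. That table gives no respiratory-rate limits by age.

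**4. Whether another criterion fills the gap.** Inclusion 37 is mandatory but has no numeric definition in the supplied text. Exclusion 10 covers actual or impending ventilation. Exclusion 15 concerns concomitant disease and investigator opinion. Exclusion 32 covers children already in hospital for COVID-19. None prints an SpO2 limit.

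**5. Which analyses depend on the reading.** The PK and safety populations (Protocol Section 2.10.3, SAP Table PYAB.6.1) are defined by dosing and, for PK, by sampling. The Per-Protocol set in the same SAP table drops anyone who met an exclusion criterion, so its membership depends on how criterion 9 is read. It is meant for sensitivity analyses of the primary and key secondary endpoints, but SAP Section 6.10.2 says additional primary-outcome analyses do not apply to this cohort.

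**The case against.** The strongest reply is that a reading in which any one sign excludes is also ordinary English. The Schedule of Activities ends its list of hospitalization events to record with 'and', and nobody would require all of those events together. The addendum's style is mixed, since inclusion 37 and several exclusions write alternatives with 'or'. This part stands: what is shown is an ambiguous rule, not proof that sites would apply the stricter reading.

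Second, inclusion 37 binds every participant and cannot be waived. A child whose disease is not mild to moderate is ineligible however criterion 9 is parsed, and investigators must confirm experience with the age range they enroll. This also stands and limits the practical risk. It does not supply a limit. Both criteria cite guidance that is not in the supplied documents, so whether an SpO2 limit already operates through the severity definition is unknown either way.

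Third, the closing words 'due to COVID-19' might govern all three signs or only the last. Rewording must not settle that silently, because it decides what happens to a child on long-term respiratory support whose usual SpO2 is ≤93%. This is accepted and carried into the fix.

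**Conclusion.** Criterion 9 needs a wording correction of low to moderate severity; confidence is moderate. As printed it can be read to exclude only a child who meets all three limits. On that reading, 3 of the 4 rate combinations with SpO2 ≤93% fall to judgement-based criteria. The conclusion rests on the printed connectives and on the assumption, drawn from the mild-to-moderate population, that SpO2 ≤93% is meant to exclude alone.

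A reader might infer three stronger things, and the documents support none of them:

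- *That the trial sets out to admit hypoxic children, or will admit many.* The likely intent is the opposite, inclusion 37 still applies, and no vital-sign distribution is given from which to estimate a share.
- *That all three signs should exclude separately at the printed limits.* A stand-alone heart rate of 125 is below the SAP's own high-pulse limit in every age band except adolescents.
- *That the main results are affected.* The PK and safety populations, sample size and power are unchanged. Only Per-Protocol membership depends on the reading.

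**What to change.** Amend criterion 9 so that either of these excludes on its own:

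- SpO2 ≤93% breathing room air at sea level;
- SpO2 ≤93% while on long-term oxygen or respiratory support for a condition other than COVID-19. The sponsor should state whether this clause applies only when the low value is due to COVID-19, so that children whose usual SpO2 is ≤93% are handled as intended.

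Do not make respiratory rate ≥30 or heart rate ≥125 stand-alone exclusions at one limit for all ages. If the rates are meant to exclude alone, the clinical team should set age-specific limits. A single limit could turn away infants and young children when the rate is attributed to COVID-19, and so hinder the planned minimum of 5 participants aged 0 to <2 years. The SpO2 change need not wait for that decision.

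The cost is a one-criterion amendment and a note to sites. No procedure, sample or visit is added, and sample size and power are unaffected. The downside is that a few children whom the all-three reading admits would be excluded. Depending on the sponsor's answer on the second clause, these may include some on long-term support.

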2.8. Section 6.1 Study Intervention(s) Administered

Treatment Arm 23

Intervention Name	LY3853113
Dose Formulation	Solution
Dosage Level(s) (mg)	See Addendum Section 2.6
Use	Experimental
IMP and NIMP	IMP
Sourcing	From Lilly
Packaging and Labeling	Study Intervention will be provided in glass vials and will be labeled appropriately.

Abbreviations: IMP = investigational medicinal product.

Dose preparation and administration information may be found in the pharmacy preparation instructions.

Participants should be monitored for at least 1 hour after completion of administration. The administration rate may be reduced as deemed necessary if an injection-related reaction is observed.

Further details will be included in the pharmacy preparation instructions. The site must have resuscitation equipment, emergency drugs and appropriately training staff available during the administration and for at least 1 hour after the completion of the administration.

2.9. Section 8.1. Efficacy Assessments

2.9.1. Section 8.1.2. Symptom Assessment for Pediatric Participants

The presence or absence of symptoms associated with COVID-19 within the past 24 hours will be collected from participants or their parents/legal guardian.

Signs and symptoms associated with COVID-19 should not be captured as AEs, unless more severe than expected.

Symptoms include

- shortness of breath or difficulty breathing
- nasal congestion or runny nose
- fever
- chills
- sore throat
- malaise
- nausea
- vomiting
- diarrhea
- cough
- tiredness
- muscle or body aches and pain
- headache
- new loss of smell
- new loss of taste, and
- poor appetite or poor feeding, especially in babies under 1 year old.

Source: FDA February 2021; CDC January 2022; CDC March 2022.

2.10. Section 9.0. Statistical Considerations

2.10.1. Section 9.1. Statistical Hypotheses

This is an open-label study with a primary objective of assessing PK and secondary objective of describing safety. The PK of bebtelovimab administered via a weight-adjusting dosing scheme is hypothesized to be well-characterized and consistent with adult exposure.

2.10.2. Section 9.2. Sample Size Determination

There is an urgent unmet need among pediatric patients since there are no approved vaccines for the prevention of COVID-19 in pediatric patients <5 years of age and no FDA-approved therapies effective for treatment of the Omicron variant in patients <12 years or outside the existing bebtelovimab EUA criteria. Consequently, this study will include SARS-CoV-2 positive pediatric patients with mild to moderate disease that are 0 (≥ 38 weeks gestational age and ≥ 3.3 kg) to <12 years of age, or 12 to 17 years of age and weighing <40 kg.

The planned sample size is approximately 50 participants that are 0 (≥ 38 weeks gestational age and ≥ 3.3 kg) to 12 years of age, with a minimum of 5 participants in each of these age groups

- 0 to <2
- 2 to <6 years, and
- 6 to <12 years

Participants who are 12 to 17 years of age and weighing less than 40 kg can be enrolled into the study until approximately 50 participants that are 0 (≥ 38 weeks gestational age and ≥ 3.3 kg) to 12 years of age are fully enrolled.

Fifty participants would provide adequate study power to target a 95% confidence interval within 60% to 140% of the geometric mean estimates of clearance and volume of distribution (Wang et al. 2012) for bebtelovimab as can be seen in [Figure 3](#).

[figure not shown]

Figure 3. Estimated study power to target a 95% confidence interval within 60% to 140% of the geometric mean estimates of clearance and volume of distribution.

The anticipated risks of bebtelovimab are low, based on the known mechanism of action for human-derived neutralizing antibodies in acute viral disease states. Bebtelovimab is a highly specific mAb directed at a foreign (nonhuman) epitope(s). The complementarity determining regions of this mAb were derived from B lymphocytes of convalescent naturally SARS-CoV-2-infected patients and thus has undergone natural positive and negative selection pressures in vivo. No clinically relevant off-target binding has been observed in tissue cross-reactivity (TCR) studies of membrane targets in human tissues. Therefore, off-target binding and TCR are considered unlikely.

The safety profile of bebtelovimab is expected to be similar to that of bamlanivimab and etesevimab based on their similar mechanism of action. Because the observed safety profile of bamlanivimab and etesevimab was similar between adults and pediatric patients, it is reasonable to expect a similar safety profile with bebtelovimab in pediatric patients. Importantly, clinical trial results of low- and high-risk adults with mild-to-moderate COVID-19 receiving bebtelovimab indicate that the observed risks are monitorable (such as infusion-related reactions, pruritis, rash that were reported in <1% of trial participants) and manageable in the clinical setting.

Efficacy will be fully extrapolated from adult data. Considering there is no expectation that risk status for severe disease has any impact on PK and safety findings, pediatric patients with mild-to-moderate disease are not required to have a risk factor for severe disease to enroll into the study. Benefit in symptom relief is a reasonable expectation for enrolling patients regardless of risk status, and the wider pool of potential participants is expected to expedite enrollment.

2.10.3. Section 9.3. Populations for Analyses

This table defines the pediatric populations for analysis.

Pediatric Population for Analysis	Description
Pharmacokinetic	All pediatric participants who received a full dose of study intervention and have at least one evaluable PK sample.
Safety	All pediatric participants who received study intervention.
Efficacy	All pediatric participants who received study intervention and provided at least one post-baseline measure for the relevant endpoint.

2.10.4. Section 9.4. Statistical Analyses

2.10.4.1. Section 9.4.1. General Considerations

Statistical analysis of this study will be the responsibility of the sponsor or its designee.

Unless otherwise specified, all endpoints will be summarized descriptively. Descriptive summaries will include

- number of participants
- mean, standard deviation, median, minimum and maximum for continuous measures, and
- frequency counts and percentages for categorical measures.

Analyses will be performed overall and separately by age group. The age groups are defined as

- 0 to <2 years,
- 2 to <6 years,
- 6 to <12 years, and
- 12 to 17 and weighing <40kg

Additional details may be provided in the statistical analysis plan.

2.10.4.2. Section 9.4.2. Primary Endpoint Treatment Arm 23

The primary objective is to assess PK in the pediatric pharmacokinetic population. The primary parameter for analysis is the area under the concentration-time curve (AUC) from 0 to infinity. Other parameters, such as half-life, apparent clearance, and apparent volume of distribution, may be reported.

2.10.4.3. Section 9.4.3. Secondary Endpoints

The secondary objective is to describe safety. The pediatric safety population is described in Addendum Section 2.10.3. Safety analyses will consist of summaries by preferred term within system organ class of treatment-emergent adverse events and serious adverse events (including reason for seriousness). The incidence of any treatment administrations that are interrupted or incomplete due to an adverse event will also be summarized, along with the incidence of immediate or non-immediate hypersensitivity events.

2.10.4.4. Section 9.4.3.4. Pharmacokinetic and Pharmacodynamic Analyses

Bebtelovimab concentration data may be analyzed using a population PK approach via nonlinear mixed-effects modeling with the NONMEM software. In addition, the effects of participant factors, such as weight, age and gender on PK parameters may be evaluated. If antidrug antibody is detected from immunogenicity testing and data are available, its impact on bebtelovimab PK may also be evaluated.

Pharmacodynamic endpoints will be summarized using descriptive methodology. The SARS-CoV-2 viral dynamics will include evaluation of

- change from baseline in SARS-CoV-2 viral load (Days 5, 7, and 11)
- AUC.

Additional PK/PD concentration-response analysis may be performed.

2.10.5. Section 9.5. Interim Analyses

An interim analysis may be conducted to evaluate safety in support of regulatory interactions. This interim may include all pediatric data available at that time and relevant analyses.

Early review of PK data may be planned but is not considered a formal interim analysis.

The approximate timing, decision criteria, and statistical methods associated with each possible modification to this study will be fully described in the statistical analysis plan.

2.10.6. Section 9.6 Assessment Committee (AC)

The sponsor will form an AC to analyze the interim safety data. To minimize any bias introduced into the conduct and analysis of the study, the addendum specific analysis plan will be approved prior to the first interim analysis.

The primary goal of the AC is to review the interim results to facilitate the safety of study participants while maintaining the validity and scientific merit of the study. Information gained

from these analyses will not be reported to study sites or the broader study team beyond the AC until the final DBL for the cohort.

Overall AC structure information is in the main PYAB Protocol Section 10.1.5. Details of the AC will be provided in the Addendum (4) SAP.

2.11. Section 10.1.11. Investigator Information

Physicians with specialties, including, but not limited to pediatrics, infectious disease, acute or critical care, pulmonary disease, immunology, or other appropriate specialties may participate as investigators for this addendum.

An investigator or sub-investigator must also confirm that they have clinical experience to adequately manage participants in a particular age range in order for the site to enroll participants in that respective age range. The age ranges are

- less than 1 year of age
- 1 to 11 years of age, and
- 12 to 17 years of age.

This addendum will be conducted at a diverse group of sites that may include academic and community affiliated outpatient clinics and emergency departments, as well as other locations where children may be seen for outpatient care. Clinicians providing care in such settings may include pediatricians, neonatologists, family practitioners, emergency room specialists, and other physicians. The investigator requirements are written to reflect this reality of pediatric patient care in outpatient settings during the pandemic.

